7.12. Drug abuse, misuse, overdose and medication errors

The adverse events or at risk scenairos including drug abuse, misuse, overdose and medical errors should be reported to the sponsor.

Abuse of a medicinal product: Persistent or sporadic, intentional excessive use of medicinal products, which is accompanied by harmful physical or psychological effects [DIR 2001/83/EC Art 1(16)].

Misuse: Intentional and inappropriate use of a medicinal product not in accordance with the prescribed or authorized dose, route of administration, and/or the indication(s) or not within the legal status of its supply.

Overdose: Administration of a quantity of study drug given per administration or per day, which is above the assigned dose.

Medication Error: An error made in prescribing, dispensing, administration, and/or use of the study drug. Medication errors are reportable to the Sponsor as defined below.

- •The dispensing, administration and/or use of the unassigned study drug.
- •The administration and/or use of an expired study drug.

Note: Cases of patients missing doses of the study drug are not considered reportable as medication errors.

AEs or SAEs associated with drug abuse, misuse, overdose, or medication error must be reported as appropriate (add appropriate section for reporting of AE)

Note: Unintentional missing drug does not belong to medical error that must be reported.

8. Patient withdrawal and replacement

8.1. End of treatment

Patients may withdraw from treatment with the study drug for any reasons at any time without providing any reasons and will not have any punishment or damages. If clinically required, the investigator may terminate treatment with the study drug for the patient at any time. The main reason for termination or discontinuation of the study drug should be confirmed according to the following classification:

- Clinical progression
- Disease progression confirmed by institutional independent radiologic review

- AE
- The patients request withdrawal from the treatment

Zai Lab

- Death
- Lost to Follow-up
- Investigator's decision
- Pregnancy
- Termination of the study by the sponsor

If the patient requests to withdraw from treatment, the investigator should try to contact the patient to confirm reasons for withdrawal and ask the patient to return to study site to receive EOT visit and safety follow-up. If the patient withdraws from the study for any reasons other than "requesting withdrawal", EOT visit, safety follow-up visit and OS follow-up visit should be carried out. Patients should return all used, partially used and unused study drugs and bottles.

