Confirmation of absence of progressive disease: if institutional independent radiologic reviewers confirm there is no progressive disease, the patient will continue to receive the study drug, unless there are medical needs requiring discontinuation of the study drug (that is, rapid progression or clinical worsening). If investigators confirm progression according to clinical worsening, imageological examination should be performed and reviewed by institutional independent radiologic reviewers to confirm whether the patient has progression. Basis for

confirming progression based on clinical worsening should be recorded in source documents and eCRF of patients. If the investigator confirms progressive disease according to "RECIST v1.1-GIST-specific Criteria", the investigator should wait for assessment and confirmation by the independent radiologic review and then terminate the patient's treatment. If the investigator doesn't hope to confirm by the independent radiologic review or hopes to terminate the patient's treatment according to progressive disease based on "RECIST v1.1-GIST-specific Criteria" before obtaining results of the independent radiologic review, it is necessary to discuss with the sponsor.

Radiographic examination of patients of various treatment groups should be performed according to the predetermined time and cycle will not be influenced by suspension or delay of treatment with the study drug. If the patient discontinues treatment for reasons other than progressive disease, death, withdrawal of consent and lost to follow-up, the patient should receive radiographic examination for tumor assessment according to the specified time interval after treatment withdrawal until progressive disease based on "RECIST v1.1-GIST -specific Criteria" or initiation of new anti-tumor therapy.

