6.10.2. Overall survival follow-up by telephone

All patients will be followed up until withdrawal of consent or death for any reason. After safety follow-up visit, patients will be contacted once every 2 months (\pm 10 days) to collect new information of anti-tumor therapy and OS data.

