8.2. End of Study

The main reason for termination or withdrawal form the study should be confirmed according to the following classification:

- Death
- Lost to Follow-up
- Termination of the study by the sponsor
- Patients will withdraw from the study

Patient withdrawal and replacement 8.3.

Patients will be not substituted in the study.

9. Statistical Consideration

9.1. **Determination of sample size**

This study will bridge foreign clinical trial (study INTRIGUE) to prove the efficacy of the investigational drug DCC-2618 (ripretinib, ZL-2307) is consistent in foreign population and Chinese population. In the study, no statistical test hypothesis is specified in advance. Statistical significance test for efficacy endpoint and multiplicity correction for multiple analysis populations will not be performed.

Approximately 98 subjects will be enrolled into the study and randomized to a test group and a control group in a 1:1 ratio. The sample size eatimation will be based on the same study hypothesis as foreign, that is, median progression-free survival (mPFS) is 9 months in the test group and 6 months in the control group. Hazard ratio (HR) of the test group to the control group is 0.667. If the study keeps \geq 50% of the overall effect size of study INTRIGUE, that is, point estimate of HR should be ≤ 0.833 , it will be considered that results of this study are consistent with those of study INTRIGUE. If 58 cases of PFS events occur, a 80% probability will be obtained and athe conclusion of consistency will be drawn with a probability of 80%. Assumeing the subjects annual drop-out rate of subjects of the total study population is 5%, approximately 98 subjects (49 for the test group and the control group, respectively) are enrolled within 7 months and followed up for 7 months, and 58 cases of PFS events will occur. Main Primary analysis based on ITT will be carried outperformed when 58 cases of PFS events occur and it is estimated that the data cutoff of the analysis will be 7 months after completing enrollment.

Zai Lab

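### Section 8.1 excepts patients who ask to stop study drug from overall-survival follow-up, contradicting Sections 6.4 and 6.10.2, the synopsis and Table 1

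*Combined protocol and SAP*

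**What the plan says.** Section 8.1 lists the reasons for ending study drug. One of them is "The patients request withdrawal from the treatment". For that patient the investigator is to find out why and "ask the patient to return to study site to receive EOT visit and safety follow-up". The next sentence covers patients who leave for any reason other than requesting withdrawal, and says "EOT visit, safety follow-up visit and OS follow-up visit should be carried out". Section 8.2 has a separate list of reasons for ending the study, which includes "Patients will withdraw from the study".

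Section 6.10.2 states: "All patients will be followed up until withdrawal of consent or death for any reason". Table 1 footnote 3 repeats this. Section 6.4 and the Study Design part of the synopsis place survival telephone calls after the safety follow-up and except nobody. The calls are every 2 months.

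On imaging, Section 6.10.1 sets the condition "If the patient discontinues treatment for reasons other than progressive disease, death, withdrawal of consent and lost to follow-up" and then requires that "the patient should receive radiographic examination for tumor assessment according to the specified time interval after treatment withdrawal", up to progression or the start of another anticancer treatment. The imaging note to Table 1 says the same.

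Section 9.5.5.2.2 censors OS at last contact for patients who are alive or lost. Section 9.5.5.1 leaves the PFS event and censoring rules to the SAP.

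**The concern.** Section 8.1 is where site staff will look when a patient says that he or she wants to stop the tablets. It names OS follow-up for every reason except this one, and between two consecutive sentences it moves from withdrawing from treatment to withdrawing from the study. Taken as the working rule, it ends survival contact for people who have agreed to stay in the study.

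OS is a secondary endpoint compared between arms. In an open-label trial, a request to stop may reflect the drug received, its tolerability or early deterioration. Censoring at that point need not be independent of prognosis, and calls that were never made cannot be recovered in the analysis.

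**Working it through.** **1. OS: the rules side by side for a patient who asks to stop drug and has not withdrawn consent**

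| Place | OS follow-up for this patient |
|---|---|
| 8.1, request sentence | Not named (EOT visit and safety follow-up only are named) |
| 8.1, next sentence | Given for all other reasons; this one is excepted |
| 6.10.2 and Table 1 footnote 3 | Yes, until death or consent withdrawal |
| 6.4 and synopsis | Yes, after the safety call, no exception |

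The passages cannot all be followed.

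**2. Does requesting withdrawal in 8.1 mean withdrawing consent?** Three features of the text count against it.
- The phrase matches an item in 8.1's own list, which concerns treatment.
- Leaving the study has its own list in 8.2.
- Without patient withdrawal, the 8.2 list leaves death, loss to follow-up and termination by the sponsor. An EOT visit followed by OS follow-up makes little sense for those. It makes sense for 8.1 reasons such as adverse event or progression. So the second sentence is about stopping treatment, despite its mention of the study.

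**3. What one affected patient loses (illustration; the timing is assumed).** Suppose the last patient enrolled asks to stop at month 3. The safety call comes about 1 month after the last dose, so contact ends near month 4. Section 3.3 allows the study to run to at most 20 months after enrolment ends. Up to 20 − 4 = 16 months of survival follow-up are lost, or 16 / 2 = 8 calls.

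**4. Imaging.** Section 8.1 names scans for no discontinuation reason, so its silence singles out nobody. The 6.10.1 exemptions are progression, death, consent withdrawal and loss to follow-up. A request to stop drug is not among them, so scans are still owed. The weak point is the coding. Section 3.3 lists consent withdrawal as a reason for treatment to end, but the 8.1 list has no such item. A patient who withdraws consent and one who only stops drug can therefore receive the same treatment-end reason, and that reason alone does not show whether scans are due.

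**5. What the plan's figures can show about PFS.** Section 9.1 gives HR 0.667, threshold 0.833, 58 events and an 80% probability of concluding consistency. With log-HR variance 4/d under 1:1 allocation:

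P = Φ[(ln 0.833 − ln 0.667) × √58 / 2] = Φ(0.846) = 80.1%, which reproduces the plan.

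Loss unrelated to prognosis hardly matters. With exponential PFS (medians 9 and 6 months) and 7 + 7 months, expected events are 59.8 at the planned 5% annual drop-out and 56.2 at 20%; the probability stays about 80%.

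Only loss that is both informative and different between arms would move it. **Purely hypothetically**, let a share q of one arm's progressions be censored instead of observed. The observed HR is then 0.667 / (1 − q) if the loss is on sunitinib, or 0.667 × (1 − q) if on ripretinib:

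| q | Sunitinib arm: HR, P | Ripretinib arm: HR, P |
|---|---|---|
| 5% | 0.702, 74% | 0.633, 85% |
| 10% | 0.741, 67% | 0.600, 90% |

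These rows assume that sites disregard 6.10.1, with a rate and an arm that the documents do not give. They are not estimates for this trial.

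**The case against.** The strongest defence has four parts.

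- **Section 8.1 never says that the named visits are the only ones.** It sends the patient to safety follow-up, and 6.4 then leads on to survival calls. This would answer a mere omission. It does not answer the second sentence, which grants OS follow-up by expressly excepting this group.
- **In a translated text, requesting withdrawal may have been meant as withdrawing consent.** If so, the OS conflict disappears. The reading is possible, but it fits neither the 8.1 item nor the separate list in 8.2. A site should not have to guess.
- **Sections 8.1 and 8.2 already classify treatment end and study end separately.** This is true, and it makes the repair easier. It does not undo the exception in 8.1, and neither list names withdrawal of consent to follow-up.
- **The PFS endpoint is protected by 6.10.1.** This stands. A reader might infer that 8.1 also ends tumour imaging and so biases the primary analysis. The documents do not support that: scans after stopping drug remain required, and clinical worsening that the investigator judges to be progression must be imaged and independently reviewed. The expected loss is also small in the plan's terms. At 5% annual drop-out, about 2.7 patients across both arms would be lost before an event, whereas 10% of one arm of 49 is already about 5.

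**Conclusion.** The plan is wrong as written on OS follow-up: this is an internal contradiction. Section 8.1 excepts patients who ask to stop drug, while 6.10.2 and Table 1 footnote 3 include them and 6.4 and the synopsis make no exception. If 8.1 is followed, each such patient is censored for OS at last contact, for a reason that may be related to arm and prognosis. The conclusion rests on reading requesting withdrawal as the treatment-stop item in 8.1, which the text favours but does not state.

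For PFS there is a risk from merged categories and nothing more. It would be going too far to say that 8.1 loses PFS outcomes or shifts the hazard ratio by a known amount. The documents give no frequency, timing or arm split of these requests, and the hypothetical shifts run in both directions. No stated figure changes, and the sample size is unaffected.

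**What to change.** Reconcile Section 8.1 with 6.4, 6.10.1, 6.10.2 and Table 1:

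1. State that a patient who stops study drug at own request, and has not withdrawn consent to follow-up, continues scheduled imaging to the end point already set in 6.10.1 and two-monthly OS contact as in 6.10.2.
2. Remove the exception for requesting withdrawal from the OS sentence, and use withdrawal from treatment and withdrawal from the study as distinct terms throughout 8.1.
3. Record withdrawal of consent to follow-up, with its date, in an eCRF field separate from the request to stop drug.
4. In the SAP, state how PFS is censored for patients who stop at own request, and include them in a sensitivity analysis. Section 9.5.5.1 already assigns both topics to the SAP.

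The cost is wording and one eCRF field. The scans and calls are already required elsewhere in the protocol, and the patient's right to withdraw is unchanged.

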8.2. End of Study

The main reason for termination or withdrawal form the study should be confirmed according to the following classification:

- Death
- Lost to Follow-up
- Termination of the study by the sponsor
- Patients will withdraw from the study

Patient withdrawal and replacement 8.3.

Patients will be not substituted in the study.

9. Statistical Consideration

9.1. **Determination of sample size**

This study will bridge foreign clinical trial (study INTRIGUE) to prove the efficacy of the investigational drug DCC-2618 (ripretinib, ZL-2307) is consistent in foreign population and Chinese population. In the study, no statistical test hypothesis is specified in advance. Statistical significance test for efficacy endpoint and multiplicity correction for multiple analysis populations will not be performed.

Approximately 98 subjects will be enrolled into the study and randomized to a test group and a control group in a 1:1 ratio. The sample size eatimation will be based on the same study hypothesis as foreign, that is, median progression-free survival (mPFS) is 9 months in the test group and 6 months in the control group. Hazard ratio (HR) of the test group to the control group is 0.667. If the study keeps \geq 50% of the overall effect size of study INTRIGUE, that is, point estimate of HR should be ≤ 0.833 , it will be considered that results of this study are consistent with those of study INTRIGUE. If 58 cases of PFS events occur, a 80% probability will be obtained and athe conclusion of consistency will be drawn with a probability of 80%. Assumeing the subjects annual drop-out rate of subjects of the total study population is 5%, approximately 98 subjects (49 for the test group and the control group, respectively) are enrolled within 7 months and followed up for 7 months, and 58 cases of PFS events will occur. Main Primary analysis based on ITT will be carried outperformed when 58 cases of PFS events occur and it is estimated that the data cutoff of the analysis will be 7 months after completing enrollment.

Zai Lab

In population with KIT exon 11 mutation, it was assumed in the foreign study that mPFS of the test group was 9 months and mPFS of the control group was 5 months, and HR of the test group to the control group was 0.556. If the study keeps \geq a 50% and of the overall effect size of study INTRIGUE in population with KIT exon 11 mutation, that is, point estimate of HR should be ≤ 0.778 , it will be considered that results based on KIT exon 11 mutation population in this study are consistent with those in study INTRIGUE. If 26 cases of PFS events occur in population with KIT exon 11 mutation, the conclusion of consistence with study INTRIGUE can be drawn with a probability of 80%.

9.2. **Study Endpoints**

9.2.1. **Primary endpoints**

The independent radiologic review will assess PFS according to "RECIST v1.1-GIST-specific Criteria" (Appendix 16.1). "RECIST v1.1-GIST-specific Criteria" assessment criteria include:

- No lymph nodes chosen as target lesions; enlarged lymph nodes will be followed as non-target lesions.
- No bone lesions chosen as target lesions;
- Positron emission tomography (PET) not acceptable for radiological evaluation;
- A progressively growing new tumor nodule within a pre-existing tumor mass must meet the following criteria to be considered as unequivocal evidence of progression according to the modification of RECIST Version 1.1: (a) the lesion is at least 2 cm in size and definitively a new active GIST lesion (e.g. enhancing with contrast or other criteria to rule out artefact); or (b) the lesion has to be expanding on at least 2 sequential imaging studies.

9.2.2. **Secondary endpoints**

9.2.2.1. **Effectiveness**

- ORR (confirmed CR + confirmed PR) based on independent radiologic review
- Disease control rate (DCR) at months 6, 9 and 12, assessed by independent radiologic review
- PFS assessed by the investigator according to "RECIST v1.1-GIST-specific Criteria"
- Overall survival (OS)

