In population with KIT exon 11 mutation, it was assumed in the foreign study that mPFS of the test group was 9 months and mPFS of the control group was 5 months, and HR of the test group to the control group was 0.556. If the study keeps $\geq 50\%$ of the overall effect size of study INTRIGUE in population with KIT exon 11 mutation, that is, point estimate of HR should be ≤ 0.778 , it will be considered that results based on KIT exon 11 mutation population in this study are consistent with those in study INTRIGUE. If 26 PFS events occur in population with KIT exon 11 mutation, the conclusion of consistence with study INTRIGUE can be drawn with a probability of 80%.

Note: If a patient has exon 11 mutation along with 1) exon 9 and/or PDGFRA mutation, the patient will be considered with exon 11 mutation at randomization. Mutation type of the patient will be defined according to a mutation with a higher MAF if the patient has mutation allele frequency (MAF) data; 2) other KIT exon mutation, the patient will be considered with exon 11 mutation at randomization.

Study duration

Patients will receive treatment until progressive disease confirmed by the independent radiologic review based on "RECIST v1.1-GIST-specific Criteria", intolerable toxicity or withdrawal of consent.

Patients will discontinue the study drug treatment if patients have progressive disease based on assessment of the independent radiologic review using

	"RECIST v1.1-GIST-specific Criteria".
	The longest medication duration of patients is 2 years. For patients with evidence of clinical benefit from the drug and tolerance to the drug and following the study procedure, the treatment duration will be prolonged by reaching an agreement between the sponsor and the investigator.
	The study will be terminated when the last patient has progressive disease or 20 months after finishing enrollment or when the sponsor determines to terminate the study, whichever occurs first.
Schedule of visits and the content thereof	Please refer to Table 1

Zai Lab

Figure 1: Schematic diagram of the study

Patients are histologically diagnosed with GIST and must have progressed during receiving imatinib treatment or intolerance.

OS DCC 2618 N = 49150 mg A treatment cycle consists of QD Screening and consecutive 42 days of dosing Safety **PFS** Random follow-up assignment Sunitinib N = 4950 mg QD 4W on/2W off 4W on/2W off, 42 days for a treatment cycle.

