Zai Lab will carry out phase 2 bridging study of the study. A study design similar to study INTRIGUE will be adopted and study population is also consistent with study INTRIGUE, that is, patients with advanced GIST who have progressed after prior imatinib treatment or are intolerant to imatinib. The GIST epidemiology, pathogenesis and clinical treatment practice in Chinese and western medicine are highly similar. If study data of DCC-2618 and INTRIGUE are consistent in Chinese GIST patients receiving the same line of treatment, it will support that DCC-2618 is used in the indication in China.

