9.5.5. Efficacy analysis

9.5.5.1. Primary endpoint: progression-free survival

The primary endpoint PFS is defined as the time interval from randomization to the earliest documented evidence of progressive disease based on assessment of the independent radiology review or death due to any causes. PFS analysis in the ITT population will be stratified by the randomization stratification factors (KIT exon 11 mutation; KIT exon 9 mutation; other (KIT/PDGFRA WT or other KIT [lacking exon 9 or 11]/PDGFRA mutation). Survival curve of different treatment groups will be plotted with KM method and the median progression-free survival (mPFS) and its 95% CI of different groups will be calculated. Under a two-sided significance level of 0.05, stratified log-rank test will be adopted to compare difference in survival curve between the two groups. Point estimate of hazard ratio will be obtained by stratified Cox regression model and relevant 95% CI will be calculated with Wald method. Randomization stratification factor is stratification factor and treatment factor is the covariant.

Rules of defining PFS events and censoring PFS will be elaborated in the statistical analysis plan (SAP). Sensitivity analysis for PFS will be specified in the SAP.

ITT population will be used as the primary analysis population in this analysis while the PP

population as supportive analysis population. Sensitivity analysis of progression-free survival will be performed, which will be further described in SAP.

Zai Lab

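### The consistency rule is worded as keeping half of INTRIGUE's effect, but its limits (HR 0.833 and 0.778) are half of INTRIGUE's planning assumptions

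*Combined protocol and SAP*

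**What the plan says.** Section 9.1 gives the aim as showing that efficacy "is consistent in foreign population and Chinese population". The sizing "will be based on the same study hypothesis as foreign": median PFS of 9 against 6 months, HR 0.667. The criterion is to keep at least 50% "of the overall effect size of study INTRIGUE, that is, point estimate of HR should be ≤ 0.833". If that is met, "it will be considered that results of this study are consistent with those of study INTRIGUE". The stated chance of meeting it is 80% at 58 PFS events.

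For KIT exon 11, "it was assumed in the foreign study that mPFS of the test group was 9 months and mPFS of the control group was 5 months", HR 0.556. The same 50% wording follows, "that is, point estimate of HR should be ≤ 0.778", with 80% at 26 events. The synopsis repeats both rules.

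Section 9.5.5.1 sets out the primary analysis: a stratified log-rank test, and "Point estimate of hazard ratio will be obtained by stratified Cox regression model". It gives no consistency criterion and does not mention INTRIGUE's observed HR. Section 1.5.1 shows what rests on the conclusion: "If study data of DCC-2618 and INTRIGUE are consistent in Chinese GIST patients receiving the same line of treatment, it will support" use of the drug in this indication in China.

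**The concern.** The rule is relative in words and absolute in numbers. Keeping half of another trial's effect needs that trial's effect, but the limits use what INTRIGUE was designed to detect. Nothing in the text says the limits will be recalculated once INTRIGUE reads out, or what happens if INTRIGUE shows a different effect or none.

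This is the only rule given for the study's stated aim. Followed literally, it compares the Chinese result with a planning assumption. Once INTRIGUE has reported, the words and the number can give opposite verdicts, and choosing between them then would be post hoc.

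**Working it through.** **Inputs (section 9.1).** Assumed medians of 9 vs 6 months (ITT) and 9 vs 5 months (exon 11); 58 and 26 events; 1:1 allocation; stated probability 80%.

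**1. Reproduce the limits.** Assumed HRs: 6/9 = 0.667 and 5/9 = 0.556. Half retention on the 1 − HR scale:

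- ITT: 1 − 0.5 × (1 − 0.6667) = 0.833
- Exon 11: 1 − 0.5 × (1 − 0.5556) = 0.778

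Both match. The plan names no scale. Half retention on the log-HR scale would give √0.6667 = 0.816 and √0.5556 = 0.745, which are not the stated limits.

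**2. Reproduce the 80%.** Pass probability = Φ[ln(limit / true HR) × √events / 2].

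- ITT: ln(0.8333/0.6667) × √58/2 = 0.2231 × 3.808 = 0.850, giving 80.2%
- Exon 11: ln(0.7778/0.5556) × √26/2 = 0.3365 × 2.550 = 0.858, giving 80.5%

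The plan's arithmetic is correct under its assumptions.

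**3. Effect kept if INTRIGUE observes something else.** Fraction kept = (1 − local HR) / (1 − INTRIGUE HR). Half-retention limit = 1 − 0.5 × (1 − INTRIGUE HR). INTRIGUE's observed HR is an assumed range.

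| Population | INTRIGUE HR (assumed) | True 50% limit | Local HR | Effect kept | Fixed rule |
|---|---|---|---|---|---|
| ITT | 0.50 | 0.750 | 0.833 | 33% | passes |
| ITT | 0.60 | 0.800 | 0.833 | 42% | passes |
| ITT | 0.75 | 0.875 | 0.86 | 56% | fails |
| ITT | 0.80 | 0.900 | 0.86 | 70% | fails |
| Exon 11 | 0.40 | 0.700 | 0.778 | 37% | passes |
| Exon 11 | 0.45 | 0.725 | 0.778 | 40% | passes |
| Exon 11 | 0.65 | 0.825 | 0.80 | 57% | fails |
| Exon 11 | 0.70 | 0.850 | 0.80 | 67% | fails |

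At an INTRIGUE HR of 0.833 the fixed ITT limit demands 100% of the effect. At 1.00 there is nothing to keep, yet a local HR of 0.833 or less still reads as consistent.

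**4. Pass probability when the true local HR equals INTRIGUE's.** Same formula as step 2, treating INTRIGUE's HR as known without error.

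| Population, events | Common HR | Fixed limit | Re-anchored limit |
|---|---|---|---|
| ITT, 58 | 0.667 | 80% | 80% |
| ITT, 58 | 0.75 | 66% | 72% |
| ITT, 58 | 0.80 | 56% | 67% |
| Exon 11, 26 | 0.556 | 80% | 80% |
| Exon 11, 26 | 0.65 | 68% | 73% |
| Exon 11, 26 | 0.70 | 61% | 69% |

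**5. Pass probability with no local effect (true HR 1, 58 events).** Limit 0.833: 24%. Limit 0.875 (INTRIGUE 0.75): 31%. Limit 0.900 (INTRIGUE 0.80): 34%.

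**The case against.** The strongest reply is that these are planning values. They sit in a sample-size section, the sentence introducing them is about sizing, the exon 11 medians are openly called assumed, and section 1.5.1 speaks of comparing study data. On that reading the verbal rule governs, 0.833 is that rule evaluated at the design HR, and only a label is missing. The ambiguity is real. But the sentence goes on to say when the results will be regarded as consistent, which is a decision rule, and no other is stated. If planning values were meant, the operative rule has still to be written.

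A second reply is that a fixed limit is prespecified and cannot loosen if the reference trial disappoints. As a minimum local effect that is legitimate, but it is not 50% retention and should be stated separately. A formula fixed before readout is equally prespecified.

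Some points stand. Any such 80% depends on its assumptions, so that alone is no defect. Section 9.1 disclaims formal efficacy testing, so no type I error claim is at stake. The HR and its 95% CI will be reported anyway, so retention can be calculated afterwards. The sizes above are illustrative because INTRIGUE's result is not given. The exact 50% match holds on the 1 − HR scale. On the log scale the limits keep 45% and 43% at the assumed HRs and would be 50% only at INTRIGUE HRs of 0.694 and 0.605, so they still depend on one particular result.

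**Conclusion.** The concern holds: the rule is wrong as written and must be fixed. The limits are correct arithmetic at HRs of 0.667 and 0.556, but they equal 50% of INTRIGUE's effect only if INTRIGUE observes those values. Otherwise the rule errs in either direction. It accepts 33–42% retention if INTRIGUE does better than assumed (ITT, 0.50–0.60) and rejects 56–70% retention if it does worse (ITT, 0.75–0.80, local HR 0.86), with a similar pattern in exon 11. It can also declare consistency with a trial that shows no effect. These figures rest on assumed INTRIGUE results and the 1 − HR scale. The pass probabilities also assume a log-HR variance of 4/events.

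**What to change.** - State that 0.833, 0.778 and the 80% are planning values conditional on the assumed HRs.
- Before either trial's results are known, define the criterion as local HR ≤ 1 − 0.5 × (1 − INTRIGUE HR). Use INTRIGUE's observed HR for independently reviewed PFS in the matching population (ITT; KIT exon 11).
- Apply it only if INTRIGUE shows a benefit in that population by a prespecified definition, for example an upper 95% confidence limit below 1. Otherwise report both HRs with intervals and draw no consistency conclusion.
- If a minimum local effect is also wanted, state it as a separate condition.
- Put the rule in 9.5.5.1 and the SAP as well as 9.1 and the synopsis.

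The cost is one prespecified paragraph in those places. Sample size, event target and HR estimation are untouched. There are two drawbacks. The numeric limit is known only when INTRIGUE reads out, and it is more lenient than 0.833 if INTRIGUE's effect is smaller than assumed (31–34% against 24% at a true local HR of 1, from step 5). That chance of passing with no effect is a separate weakness of a point-estimate rule with few events. Re-anchoring does not remove it, and it can be disclosed beside the 80%.
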